7.1. Recruitment

Throughout the 30-month enrollment period, a variety of recruitment strategies were used to identify eligible participants for the ACCESS trial, which we have classified into five overarching strategies and 14 sub strategies (Table 1). Participants who called the survey unit were asked an open-ended question to determine how they learned about the study. Responses to this question were allocated to one of the 14 sub strategies.

From November 2015 until study completion a total of 12,342 people called the survey unit (Fig. 1). Of these potential participants, 4768 were randomized.

Recruitment for ACCESS was time-consuming and costly, but ultimately successful. We used 14 sub strategies to recruit the first 4013 participants into the study, at a cost of \$354,330 CAD, which was approximately 20% of the overall study operating expenditures during this period. Despite eventual success, there was a lack of adequate planning and budgeting at the beginning of the study to successfully reach the target number of participants. Initial planning set out 12 months for recruitment, with only \$20,000 CAD set aside as a dedicated recruitment budget to contact pharmacies, which was to be the sole recruitment strategy. As recruitment continued, the timeline had to be extended and considerably more resources had to be put towards recruitment—all the other strategies developed once it became clear that the initial plans for recruitment were going to be inadequate. No single strategy appeared to succeed in recruiting typically under-represented groups; rather, the strategies differed in their ability to recruit various types of people (46,47).

7.2. Baseline Characteristics

Baseline characteristics will be reported in a Table using descriptive summary statistics. These will be stratified by group assignment, and t-tests/Chi2 tests will be used to examine for inter-group differences in these characteristics.

8. Data Sources

The main data source for the trial will be the ACCESS trial RedCAP database. This contains participant group assignments and all patient reported measures from baseline, 6-month, 18-month, and 33-month surveys. It also contains individuals' unique provincial health number which will permit deterministic linkage to administrative health databases held by Alberta Health (including Alberta Precision Laboratory data, Pharmacy Information Network Data, Practitioner Claims data, Discharge Abstract Database, National Ambulatory Care Reporting System data). All PHNs were verified at the time of study enrollment to be sure that they were accurate and active. In cases where a deterministic linkage is not possible, probabilistic linkage using name, date of birth, and postal code will be used.

9. Interventions (s)

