We confirmed the need for the current study after presenting this evidence to Alberta Health and after completing systematic reviews of interventions to address these barriers. The systematic reviews assessed: 1) the effectiveness of reducing copayments for high-value drugs in people with chronic diseases and determined that reducing copayments may result in improved adherence to medical therapy (5); and 2) the impact of 11 quality improvement strategies for diabetes and determined that the most effective strategies were patient education and facilitated relay of information by patients to clinicians (6). Neither review could determine the impact of the interventions on clinical outcomes or costs – because available evidence consisted mostly of observational studies, or because trials were short-term and used surrogate endpoints.

2. Background and Rationale

What is the problem to be addressed?

Cardiovascular disease is the leading cause of death in Canada: Cardiovascular disease claimed over 69,500 lives in Canada in 2008 (7), most as a result of cardiovascular events, such as strokes and myocardial infarctions. Cardiovascular disease is also the leading cause of hospitalization for Canadians (8). Important risk factors for cardiovascular events include prior stroke or myocardial infarction, chronic kidney disease, heart failure, diabetes or hypertension (henceforth referred to simply as “chronic diseases”). These conditions lead to severe morbidity and cost the Canadian healthcare system over \$93 billion per year (1).

Many patients with chronic diseases do not receive guideline-recommended therapy: Lifestyle modification (i.e. weight loss, exercise, healthy diet, and smoking cessation) as well as adherence with pharmacologic management are particularly important in the management of patients with chronic diseases (9–13). In Alberta, our group has documented that 50% of Albertans with these chronic diseases are not receiving guideline-recommended drugs (statins), due to a combination of patient, provider and health system level barriers (3). Our recent survey of nearly 2,000 Western Canadians suggests that patient-borne cost of prescription drugs as well as patient and provider-level knowledge gaps, are major barriers to optimal medical management (3).

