10.1. Covariate Adjustment

Consistent with usual practice, we will only adjust the primary analysis for stratified variables (age (</>70; sex and low-income status) (48).

Assuming that randomization has worked, and we have approximately equal distribution of sociodemographic and clinic characteristics between randomization groups, we will not adjust our analyses for covariates, as this should have been dealt with through the process of randomization. If there is imbalance in important covariates between randomization groups, a sensitivity analysis will be conducted statistically adjusting for these imbalanced covariates through the modelling process.

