10.4. Analysis Methods- Primary Outcome

Consistent with an intention-to-treat analysis, we will categorize all participants by their randomization group, regardless of compliance (intention-to-treat), in our primary analysis. For those participants who are no longer actively receiving the self-management intervention or completing follow-up surveys, as permitted by CHREB, we plan to use available health administrative data until the time of death or outmigration from the province.

A Poisson model will test the main effects of the impact of the interventions on the rate of the primary outcome. This technique was chosen as individuals may experience multiple outcomes prior to the end of the study period, therefore we will account for both number of events and varying observation time within the Poisson model (by using an offset to account for losses to follow-up). The likelihood ratio test will test a negative binomial regression model within the Poisson model to examine for the presence of overdispersion. If present, negative binomial models will be used.

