10.8. Planned Subgroup Analyses

We have a priori specified particular subgroup analyses, considering the biological plausibility for subgroups. We will conduct analyses stratified by subgroup, as described in the primary and secondary outcomes sections. We will provide effects with confidence intervals for subgroups (rather than p-values), as tests of interactions for subgroups can fail to detect important effects. These will be presented in a forest plot (49,50).

The subgroups of interest include:

Gender: Men vs Women (self-reported), likely exclude gender diverse

Age: >70 years vs 65-69 years

Income group: <30,000 vs >30,000

Financial barriers: Present vs Absent

Condition type: Diabetes // CKD // ASCVD // Risk factors only

Multimorbidity: 1-2 vs 3-4 indicated conditions

Primary Care Relational Continuity: Low/Medium vs High

Specialist Involvement in the year prior to randomization: Yes vs No

On statin at baseline: Yes vs No

On ACE/ARB at baseline: Yes vs No

Living environment: supported living vs. Independent living

Baseline medication adherence: >80% PDC for all covered meds vs <80% for any covered med

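### Adjusting the primary rate model only for the stratifiers, with other covariates admitted on undefined imbalance, is valid but gives up precision and leaves the sensitivity model to chance

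*Combined protocol and SAP*

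**What the plan says.** All references are to the combined protocol and SAP unless stated otherwise.

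- **Primary model (10.1):** "we will only adjust the primary analysis for stratified variables", namely age at the 70-year cut, sex and low-income status. The reason given for going no further is: "we will not adjust our analyses for covariates, as this should have been dealt with through the process of randomization".
- **Trigger for more (10.1):** "If there is imbalance in important covariates between randomization groups, a sensitivity analysis will be conducted statistically adjusting for these imbalanced covariates". There is no covariate list, no cut-off, and no definition of important or of imbalance.
- **Baseline comparison (7.2):** "t-tests/Chi2 tests will be used to examine for inter-group differences in these characteristics". No threshold is stated, and nothing in 7.2 or 10.1 ties these tests to the trigger.
- **Model form (10.4):** Poisson with an offset, then a test for overdispersion: "If present, negative binomial models will be used".
- **Predictors the plan already recognises:** section 2 states "Important risk factors for cardiovascular events include prior stroke or myocardial infarction, chronic kidney disease, heart failure, diabetes or hypertension". Section 10.8 defines subgroups by "Condition type: Diabetes // CKD // ASCVD // Risk factors only" and "Multimorbidity: 1-2 vs 3-4 indicated conditions", and also by specialist contact in the year before randomization. Section 8 links participants to hospital discharge, claims, laboratory and dispensing data.
- **Sensitivity analyses (10.9):** none is a pre-specified prognostic adjustment.

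The separate SAP for the secondary-outcome paper also adjusts only for the stratifiers (7.3). It has no baseline group tests (7.1) and no imbalance trigger.

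**The concern.** After concealed randomization, any baseline difference between groups is due to chance, so a significance test of that difference answers no useful question. Observed imbalance is also a poor reason to choose a covariate. What makes a covariate worth including is that it predicts the outcome, and that can be judged in advance.

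The rationale in 10.1 treats randomization as if it did all the work of adjustment. Randomization removes systematic confounding. It does not remove the variation between people in event rate that known risk factors explain. In a rate model with overdispersion, that variation stays in the error term and widens the interval for each intervention.

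Two things are at stake: the precision of the primary estimate, and whether the covariate-adjusted sensitivity analysis is fixed in advance or chosen after the groups have been compared.

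**Working it through.** **1. The plan's own sample size.** Inputs from 4.8: 0.14 events per participant-year, 3 years, rate ratio 0.88, alpha 5% (taken as two-sided), power 80%, 1:1 allocation. The Poisson-regression formula cited there gives

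N = [1.96·√4 + 0.8416·√(2 + 2/0.88)]² / (3 × 0.14 × (ln 0.88)²) = 4667,

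and 4667 × 1.01 = 4714. Both stated figures reproduce. The calculation assumes no overdispersion.

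**2. Dispersion implied by the plan's figures.** The mean count over 3 years is 3 × 0.14 = 0.42. A Poisson count with that mean gives 1 − exp(−0.42) = 34% with at least one event, but 4.8 reports a 26% risk. For a negative binomial, solve (1 + 0.42k)^(−1/k) = 1 − risk:

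- risk 26%: k = 2.10
- risk 28% (assumption): k = 1.44
- risk 30% (assumption): k = 0.89

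The higher risks are included because the 26% figure, as worded, omits revascularization while the rate of 14 per 100 includes it. A risk that matched the rate could be higher, and k lower.

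**3. Precision from prognostic covariates.** Per side of one factor, the variance of the log rate ratio is proportional to V = 1/0.42 + 1/0.3696 + 2k(1 − f). Here 0.3696 = 0.42 × 0.88, and f is the share of dispersion removed by the added covariates. The first two terms sum to 5.087. The range f = 20 to 40% is an assumption; the documents give no prognostic effect sizes.

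| k | V at f = 0 | V at f = 20% | V at f = 40% | Variance reduction | Interval narrower by |
|---|---|---|---|---|---|
| 2.10 | 9.287 | 8.447 | 7.607 | 9.0 to 18.1% | 4.6 to 9.5% |
| 1.44 | 7.965 | 7.390 | 6.814 | 7.2 to 14.5% | 3.7 to 7.5% |
| 0.89 | 6.872 | 6.515 | 6.158 | 5.2 to 10.4% | 2.6 to 5.3% |
| 0 | 5.087 | 5.087 | 5.087 | 0 | 0 |

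The interval column is 1 − √(1 − variance reduction). At N = 4714 (2357 per side), Wald power is Φ(0.1278/√(V/2357) − 1.96). It rises from 53% to 57–61% at k = 2.10, from 66% to 68–71% at k = 0.89, and stays at 79% at k = 0.

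These k values come from marginal figures. The stratifiers will already absorb some of the dispersion, so the upper end is generous.

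**4. How far an imbalance trigger depends on chance.** Suppose, for illustration only, that the trigger were p < 0.05 on 20 characteristics; the plan states neither. The chance of at least one flag is 1 − 0.95^20 = 64% for one intervention if the tests are independent, and 42% by simulation at a correlation of 0.5. With 4768 randomized (7.1), about 2384 per side, a 50% characteristic is flagged at 1.96 × √(2 × 0.25/2384) = 2.8 percentage points.

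**5. How much an unflagged imbalance could move the estimate.** Take a factor with 40% prevalence, an event-rate ratio of 2 to 3 and an imbalance of 2.5 points (all assumptions). The rate ratio shifts by [1 + 0.4125(r − 1)]/[1 + 0.3875(r − 1)] = 1.018 for r = 2 and 1.028 for r = 3. On the log scale that is 0.018 to 0.028. The standard error at k = 2.10 is √(9.287/2384) = 0.062, so the larger shift is under half a standard error.

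**The case against.** Adjusting for the stratifiers alone is pre-specified, and 10.1 supports it as usual practice with a reference. Wider adjustment is an efficiency choice, and the imbalance rule touches only one sensitivity analysis. All of this stands.

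A reader might infer three stronger things that the documents do not support.

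- **That the tests in 7.2 select the covariates.** Section 10.1 never says so, and its word for the covariates concerned, important, may well mean prognostic. What remains is that imbalance is still the condition for entry, whoever judges importance, and after valid randomization imbalance arises by chance.
- **That the primary result is biased or its type I error inflated.** Randomization protects it. A chance imbalance of the size in step 5 is already covered by the confidence interval.
- **That the omitted variables are known to be the strongest predictors.** Section 2 names disease risk factors without effect sizes. It does not mention prior admissions or continuous age, and age already enters at the 70-year cut.

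The gain also rests on an assumed f and an approximate k. Timing matters too: the Introduction of the separate SAP reports that results for both interventions are known, so a new primary model chosen now would itself be post hoc.

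**Conclusion.** The point holds as one of efficiency and pre-specification, not validity. Section 10.1 leaves out of the primary model risk factors that the plan itself names and already derives or can link. It lets them into a sensitivity model only on an undefined, chance-driven condition.

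With k between about 0.9 and 2.1 and 20 to 40% of the dispersion explained, the cost is about 5 to 18% of the variance of the log rate ratio, or about 3 to 9% of interval width. If the counts are truly Poisson there is no loss. The plan's 26% risk against the 34% expected under Poisson, and its own provision for negative binomial models, make some overdispersion likely. The change is worth making because it is cheap; the trial's primary conclusion does not depend on it.

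**What to change.** 1. **Section 7.2:** delete the t-tests and chi-square tests and report descriptive statistics by group.
2. **Section 10.1:** replace the imbalance trigger with a fixed list used whatever the observed balance: the stratifiers, continuous age, diabetes, CKD and ASCVD (each yes/no), and the number of admissions in the year before randomization from the linked discharge data.
3. **Where to use it:** in the primary model if the list is fixed before outcome data are seen, with the stratifier-only model kept as a sensitivity analysis. Otherwise keep the stratifier-only model as primary and run the fixed list as the sensitivity model, labelled post hoc if results are already known.

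The cost is revised wording, a few derived baseline variables from data the plan already links, and slightly more analysis work. No new data are needed and the sample size of 4714 is unchanged.

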9.1. Handling of Withdrawn Participants

A small proportion of ACCESS trial participants contacted the study coordinating centre and requested to be withdrawn from the trial.

Where individuals requested full withdrawal of all study data, they will be excluded entirely. However, in most cases, those requesting withdrawal simply wanted to receive no further contact from the study but did not specifically ask to have their data withdrawn.

For the outcomes relying upon administrative data, we will use outcome data for all withdrawn participants. For the patient-reported outcomes we will use the responses provided to the time of withdrawal and will use multiple imputation methods for the missing datapoints thereafter (See 10.3).

10. Analysis Methods

10.1. Covariate Adjustment

Consistent with usual practice, we will only adjust the primary analysis for stratified variables (age (</>70; sex and low-income status) (48).

Assuming that randomization has worked, and we have approximately equal distribution of sociodemographic and clinic characteristics between randomization groups, we will not adjust our analyses for covariates, as this should have been dealt with through the process of randomization. If there is imbalance in important covariates between randomization groups, a sensitivity analysis will be conducted statistically adjusting for these imbalanced covariates through the modelling process.

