#### **5.5.Randomization**

Using a scheme developed within REDCap by the University of Calgary's clinical research unit, randomization was completed using random small (<8) variable permuted blocks. This method will ensure robust allocation concealment. Randomization was stratified based on age (</≥70 years), gender (man/woman), and low household income status (defined by household-size specific Low-Income Cut-offs).

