### 7.3. Covariates

Considering randomization was successful, only Age, Sex, and Income status will be used for adjustment because these were the variables upon which the randomization was stratified. The literature also recommends this practice to improve discriminatory power.

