4.4. Secondary Outcomes

- 1) each individual component of the primary endpoint
- 2) medication adherence for selected medications as defined below
- 3) overall quality of life as measured by the Euroqol EQ5D-5L
- 4) the cost of the interventions and other costs relevant to the health care system assessed in a concurrent economic evaluation.

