4.7. Randomization

The University of Calgary Clinical Research Unit developed the computer-generated randomization scheme within REDCap.

Randomization was completed using random small (<8) variable permuted blocks. This method will ensure robust allocation concealment. Randomization was stratified based on: age (</≥70 years); gender (man/woman); and low household income status (defined by household-size specific Low-Income Cut-offs).

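### The randomization strata are written into the primary and cost models and into the later SAP, but into no other between-group model of the combined protocol and SAP

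*Combined protocol and SAP*

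**What the plan says.** Both documents describe the same stratified permuted-block scheme. Section 4.7 of the combined protocol and SAP states: "Randomization was stratified based on: age (</≥70 years); gender (man/woman); and low household income status". Section 5.5 of the SAP agrees, and both define low income by household-size-specific cut-offs.

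The adjustment rule is in section 10.1 of the combined document: "we will only adjust the primary analysis for stratified variables", which it lists as age, sex and low-income status. The next paragraph, assuming randomization has worked, adds: "we will not adjust our analyses for covariates, as this should have been dealt with through the process of randomization". It allows a sensitivity analysis if important covariates are imbalanced.

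The other analyses in the combined document are specified as follows:
- **Components of the composite:** listed in 4.4 as "each individual component of the primary endpoint". They have no model of their own in 10.5.
- **EQ-5D:** mixed models in 6.3 and linear regression in 10.5. Neither names strata.
- **Adherence:** log-binomial regression in 10.5, no strata named.
- **Self-efficacy and concerns:** logistic regression in 10.5, no strata named.
- **Mortality, MACE and ACSC hospitalization:** Cox models in 10.6, no strata named.
- **Costs:** section 12 adds a gamma model that does control for the stratification variables.

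The SAP, written for a later secondary paper on adherence, beliefs and self-efficacy, says in 7.3 that "only Age, Sex, and Income status will be used for adjustment because these were the variables upon which the randomization was stratified". It does not confine this to a primary analysis.

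**The concern.** Stratified randomization balances the arms on the strata. A model that leaves the strata out takes no credit for that balance. Its standard error still contains the between-stratum variation that the design removed from the treatment comparison. Intervals then come out too wide and tests reject less often than their nominal level. Here the omission would cover nearly every secondary and exploratory clinical comparison in the combined document.

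There is also a specification gap. Where a plan is explicit about strata in some models and says nothing in others, two analysts could fit different models to the same data.

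**Working it through.** **1. The plan's own figure.** Inputs from section 4.8: 14 events per 100 participant-years, 12% relative reduction (rate ratio 0.88), alpha 5%, 80% power, 1:1 allocation, 3 years. Two-sided testing is assumed. The Poisson-regression formula for a balanced binary covariate is

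N = [1.960·√V0 + 0.8416·√V1]² / (0.14 × 3 × (ln 0.88)²),

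with V0 = 4 and V1 = 2 + 2/0.88 = 4.2727.

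- Numerator: (3.9199 + 0.8416 × 2.0671)² = 5.6596² = 32.031.
- Denominator: 0.42 × 0.016341 = 0.0068634.
- N = 4666.97, so 4667. Adding 1%: 4667 × 1.01 = 4713.67, so 4714.

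The stated figure is reproduced, and adding strata to other models does not change it.

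**2. Continuous outcome (EQ-5D).** Let R² be the share of outcome variance explained by the strata. It is an assumption. In a linear model without strata:

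- excess interval width = 1/√(1 − R²) − 1
- actual size of a nominal 5% test = 2·[1 − Φ(1.96/√(1 − R²))]
- power when the adjusted analysis has 80% = Φ(2.8016 − 1.96/√(1 − R²)), where 2.8016 = 1.960 + 0.8416

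| R² | √(1 − R²) | Excess width | Actual size | Power |
|---|---|---|---|---|
| 0.02 | 0.9899 | 1.0% | 4.8% | 79.4% |
| 0.05 | 0.9747 | 2.6% | 4.4% | 78.5% |
| 0.10 | 0.9487 | 5.4% | 3.9% | 76.9% |

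A simulation under no effect (eight equally likely strata, blocks of four, 2,000 participants, 6,000 replicates) gave unadjusted rejection rates of 4.98%, 4.55% and 3.95%. With strata in the model the rates were 5.18%, 5.27% and 4.93%, which is the nominal level within simulation error.

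**3. Infrequent binary outcome.** Assume three binary factors forming eight equal strata, each factor multiplying risk by r, with overall risk p. Then

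R² = {[2(1 + r²)/(1 + r)²]³ − 1} × p/(1 − p).

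- r = 1.3, p = 0.05: 0.0519 × 0.0526 = 0.0027, excess width about 0.1%.
- r = 2.0, p = 0.10: 0.3717 × 0.1111 = 0.0413, excess width about 2.1%.

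This treats the comparison as a difference in proportions, so it shows the order of magnitude only.

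**4. Cox models.** Take a conditional hazard ratio of 0.88 (borrowed from 4.8), the 26% three-year risk in 4.8, and the large assumption that each factor doubles the hazard. Relative hazards are then 1, 2, 4 and 8 with weights 1/8, 3/8, 3/8 and 1/8. A baseline cumulative hazard of 0.0944 gives control survival 0.7400. Multiplying it by 0.88 gives 0.7659. The ratio of marginal cumulative hazards is ln 0.7659 / ln 0.7400 = 0.2667/0.3011 = 0.886. The unadjusted estimate shifts from 0.88 to about 0.886.

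**5. How the factors are named.** The age split is below 70 against 70 and over in 4.7 and in SAP 5.5, below against above 70 in 10.1 (leaving age exactly 70 in neither group), and up to 70 in section 12. Gender in 4.7 and SAP 5.5 becomes sex in 10.1, section 12 and SAP 7.3. SAP 7.3 speaks of income status without defining it. The income subgroups in SAP 7.4 and in 10.8 use a cut at 30,000, which is not the randomized stratum.

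**The case against.** The strongest reply is about the word *only* in 10.1. It may mean that the primary analysis is adjusted for the strata and nothing else. The sentence that declines covariate adjustment speaks of our analyses, which include the primary one, so it fits the sentence before it best if covariates means variables beyond the strata. The cost model and SAP 7.3 sit well with that reading. This stands. A reader might infer that 10.1 expressly excludes the strata from the secondary models, but it does not say so. Even so, on the milder reading those models still have no stated strata terms.

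Four other stronger readings are tempting and not supported:
- **That the two documents contradict each other on one adherence analysis.** The SAP serves a later paper, and the definitions differ in part. Section 6.2 uses the first 12 months and the interval between renewals, while SAP 5.3 uses days covered in a period of interest. Different adjustment for the two reports is untidy, but it is not a proven conflict over one estimate.
- **That the wrong variable will be used.** Sex appears in lists of the stratification variables and most plausibly means the man/woman stratum. No separate sex variable is shown, and no numerical effect follows.
- **That the Cox and logistic estimates are biased toward no effect.** The shift is non-collapsibility: the unadjusted ratio estimates a marginal quantity. Step 4 shows a small shift for the hazard ratio even under a large assumption.
- **That false positives increase.** The direction is the opposite.

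Timing also counts. Section 4.11 planned completion of the final analysis by July 1, 2022, and the SAP introduction reports the main trial findings as known. Changing the covariates of finished analyses now would be a choice made after seeing results. That limits the remedy but does not remove the gap.

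**Conclusion.** The point holds as a small specification gap. Section 10.1 names stratification adjustment for the primary analysis, section 12 and SAP 7.3 also adjust, and no strata are stated for the components, adherence, EQ-5D, self-efficacy and concerns, or the Cox models. Read literally, those analyses are slightly conservative. For EQ-5D the excess interval width is about 1% to 5%, and the cost is about 0.6 to 3.1 percentage points of power from 80%, for an assumed R² of 2% to 10%. These percentages come from a linear model and should not be carried over to the count, binary or Cox analyses, where the size depends on the variance estimator and the event frequency. The primary analysis and the sample size are unaffected. The differing names and age cuts are matters of wording, to be settled at the same time.

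**What to change.** In section 10.1, state that all between-group models for the primary, secondary, patient-reported and Cox analyses include the stratification factors as coded at randomization: age below 70 or 70 and over, gender (man or woman), and household-size-specific low income. Use the same variable names and the same age cut in SAP 7.3, section 10.1 and section 12.

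For results already analysed, keep the reported analysis and add the stratum-adjusted version as a labelled supplementary analysis.

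The cost is a few lines of text and some refitted models. The factors were needed to randomize, so no new data are required and the sample size does not change.
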